7.2 Screening and Baseline Procedures and Assessments

All screening evaluations must be completed and reviewed to confirm that potential patients meet all eligibility criteria, before entering the trial. The Investigator will maintain a screening log to record details of all screened participants and to confirm eligibility or record reasons for screening failure, as applicable.

7.2.1 Informed Consent

The Investigator or designated trial personnel will explain the nature of the trial and its risks and benefits to the patient. The patient must voluntarily provide written informed consent on an ethics-approved ICF, prior to any trial-related procedures are performed. The consent process must be documented in the patient's medical record, and include confirmation that the patient was given adequate time to ask the Investigator (or designee) questions about their participation in the trial and that a signed and dated copy of the ICF was provided to the patient.

7.2.2 Demographics

Age, sex, race and ethnicity will be recorded at screening.

7.2.3 Medical History

Relevant medical history within 5 years before screening and any clinically significant medical history more than 5 years before screening will be collected based on available medical records and patient interview. Data will include PLD-related history data and medical history related to gallbladder diseases. The Investigator will evaluate all findings on medical history for clinical significance. Historical liver and kidney volumes, the latter only in patients with confirmed ADPKD, will be collected if available in medical records.

7.2.4 Medication/Treatment History

All medications (prescription and non-prescription, herbal medications/natural health products, or investigational drugs) and non-pharmacological treatments taken by the patients during the 3 months before screening will be recorded in the source documentation as medication history. Pharmacological and non-pharmacological treatments taken prior to the 3 months before screening should be recorded as medical history if relevant as per the Investigator's opinion, except for history of sclerotherapy which will be recorded if occurring within at least 6 months before screening. The Investigator will determine if the prior medication(s) affect the patient's eligibility to participate in the trial.

Treatment history for PLD and related symptoms, including prophylactic treatment, will be recorded and followed up during the course of the trial.

7.2.5 Physical Examination

A physical examination including all major body systems (general appearance, skin, neck, including thyroid, eyes, ears, nose, throat, lungs, heart, abdomen, back, lymph nodes, extremities and nervous system) will be performed at the time points indicated in [Table 3](#). Clinically significant findings that were present prior to signing of the ICF must be included on the Medical History eCRF page. Significant findings that begin or worsen after signing of the ICF must be recorded on the AE page of the eCRF.

Height, weight and body mass index will be measured/calculated at screening. Weight will also be measured at the time points indicated in [Table 3](#).

7.2.6 Serology

Samples to assess hepatitis B surface antigen, hepatitis C virus antibodies (PCR required for hepatitis C virus antibody-positive patients), human immunodeficiency virus and human immunodeficiency virus antibodies will be taken at screening.

7.2.7 Contraceptive Requirements

Women of childbearing potential must agree to use an acceptable method of birth control as defined in the ICF from screening and throughout the trial and must agree to be tested for pregnancy. Acceptable method(s) of birth control include:

- Total abstinence (when this is in line with the preferred and usual lifestyle of the patient). Periodic abstinence (e.g., calendar, ovulation, symptothermal and post-ovulation methods) and withdrawal are not acceptable methods of contraception.
- Female sterilization (has had surgical bilateral oophorectomy with or without hysterectomy), total hysterectomy or tubal ligation at least 6 weeks before screening. In the case of oophorectomy alone, the reproductive status of the woman must be confirmed by follow-up hormone level assessment.
- Male sterilization (at least 6 months prior to screening). The vasectomized male partner should be the sole partner for that patient.
- Barrier methods of contraception: female condom with or without spermicide; or cap, diaphragm or sponge with spermicide. Simultaneous use of male and female condoms with or without any other contraception method is not permitted.
- Use of a non-hormonal intrauterine device or hormonal intrauterine device not containing estrogen.
- Use of oral contraceptives not containing estrogen.
- Women are considered post-menopausal and not of childbearing potential if they have had 12 months of natural (spontaneous) amenorrhea with an appropriate clinical profile (i.e., appropriate age, history of vasomotor symptoms) or have had surgical bilateral oophorectomy (with or without hysterectomy), or tubal ligation at least 6 weeks prior to screening. In the case of oophorectomy alone, the woman is considered not to be of childbearing potential only when the reproductive status of the woman has been confirmed by follow-up hormone level assessment.

Male patients must agree to use condoms for the duration of the trial, unless they have been sterilized by vasectomy (with an appropriate post-vasectomy documentation of the absence of sperm in the ejaculate).

7.3 Efficacy Assessments

7.3.1 Assessments of Liver and Kidney Volume and Total Liver Cyst Volume

MRI of the abdomen and pelvis will be performed to capture images of the kidney and liver within 4 weeks prior to Day 1 Visit ([Table 3](#)). Also historical MRI assessments can be considered as the baseline images for this trial if they fulfil the imaging and schedule requirements.

For the determination of patient eligibility at screening (i.e., htTLV ≥ 1800 mL/m), the site will calculate htTLV according to preferred method (i.e., local clinical practice or central reading) either using the MRI at screening or based on available historical imaging data.

The images will be sent to a central imaging laboratory for blinded, independent reading to determine the liver and kidney volumes and the total liver cyst volume. The volumes will be calculated as per central imaging laboratory recommendations. Imaging parameters will be recorded in the source documents and eCRF. To minimize the risk of inter- and intra-subject variation in MRI, minimum scanning parameters will be provided to each site to comply with the central imaging laboratory requirements.

The processes for image collection transmission of images to the central imaging laboratory will be described in a site manual. The central review and determination of liver and kidney volumes and total liver cyst volume will be further described in an imaging charter.

At screening, Week 77, Week 125 and Week 173/End-of-Treatment the scheduled MRI can be used for the safety assessment of the gallbladder if captured images are of satisfactory quality ([Section 7.6.7](#)).

7.3.1.1 Reporting of Incidental Findings

If incidental findings are detected on the images that may be important for further clinical evaluation, this needs to be reported in the eCRF (as medical history if the finding occurs at screening, otherwise as an AE). Patients will be informed of any relevant incidental finding during the trial, as judged by the Investigator. Findings must be handled according to normal clinical practice and followed up as determined by the Investigator.

7.3.1.2 Assessments of Selected Muscle and Adipose Tissue Areas

Scheduled MRI scans will also be used for determination of selected areas of muscle and adipose tissues where available and at time points indicated in [Table 3](#).

7.3.2 Estimated Glomerular Filtration Rate

Blood samples for assessment of the eGFR will be taken at time points indicated in [Table 3](#). The eGFR will be assessed by the CKD-EPI cystatin C equation using serum concentrations of creatinine and cystatin C. Details of the assessments will be provided separately.

7.3.3 Patient Reported Outcomes

PROs for assessment of patients' PLD-related symptoms, impact on functioning and well-being, health-related quality of life and satisfaction include:

- PLD-S Measure
- PLD-I Measure
- PGI-S
- PGI-C
- SF-36
- PLD-Q
- [REDACTED]
- [REDACTED]

- Patient Reported Outcome Validation Battery

The PROs should be administered in the patient's local language. Patients should be given enough space and time to complete the questionnaires.

The Investigator should not encourage the patient to change responses reported in the questionnaires. If a patient refuses to complete a questionnaire, this should be documented in the source records. A patient's refusal to complete trial questionnaires should not be captured as a protocol deviation.

The PROs will be completed as indicated in Table 3 and should preferably be completed at the beginning of the visit before any tests or treatments are performed and before the patient receives results from any tests to avoid biasing the patient's perspective.

7.3.3.1 Polycystic Liver Disease Symptoms

The PLD-S is a PRO currently under development to assess patient reported symptoms of PLD. The measure was developed following FDA guidance for the development of PROs, (41).

7.3.3.2 Polycystic Liver Disease Impact

The PLD-I is a PRO currently under development to assess patient reported impacts of PLD. The measure was developed following the FDA guidance for the development of PROs, (41).

7.3.3.3 Patient Global Impression of Severity

The PGI-S assessment is a self-rated measure to assess the patients' overall perception of their condition. The PGI-S for the Symptom measure is a 1-item questionnaire that asks the patient to rate the frequency of their overall symptoms over the past week. The PGI-S for the Impact measure is 4 items assessing the frequency of the impact of their PLD over the past week on overall quality of life and for each of the PLD-I measure domains (physical functioning, day to day activities, emotional well-being). The PGI-S questions use a 5 option Likert scale ranging from none at all to all of the time. The Patient Global Impression scale is the PRO counterpart to the Clinical Global Impressions scale, which was published in 1976 (42). A modified version of the PGI-S will be used.

7.3.3.4 Patient Global Impression of Change

The PGI-C is a self-report measure asking the patient to rate the efficacy of treatment (change in frequency of occurrence) since the start of trial treatment. The PGI-C for the Symptom measure is 1 item assessing the overall change in frequency of experiencing PLD symptoms and the PGI-C for the Impact measure is 4 items assessing change in frequency of experiencing overall impact on overall quality of life and for each PLD-I domain (physical functioning, day to day activities and emotional well-being). The PGI-C questions use a 5 option Likert scale ranging from much less often to much more often. The Patient Global Impression scale is the PRO

counterpart to the Clinical Global Impressions scale, which was published in 1976 (42). A modified version of the PGI-C will be used.

7.3.3.5 Short Form-36

SF-36 is a widely used standardized measure of health status (43). SF-36 will be used to assess self-perceptions of general health functioning across multiple dimensions (including general, physical, and emotional/psychiatric functioning). Higher scores indicate better quality of life. It comprises a physical component summary and a mental component summary, both for which a higher score indicates better health status.

7.3.3.6 Polycystic Liver Disease Questionnaire

[figure not shown]
The PLD-Q was developed to capture patient-reported frequency and degree of discomfort for 16 different PLD associated symptoms (20, 21). The score of each patient-reported symptom included in the PLD-Q can be calculated by adding a frequency (Likert scale; 1=never, 6=always) and discomfort (Likert scale; 0=not at all, 5=a lot) score of each symptom. Total scores will be transformed into a score ranging from 0 to 100 points, where a higher score represents a higher symptom burden. A modified version of the PLD-Q will be used.

7.3.3.7

7.3.3.8

7.3.3.9 Patient-Reported Outcome Validation Battery

In order to psychometrically validate the PLD-S and the PLD-I, additional PRO measures/individual items needed to conduct the psychometric testing will be included in the trial as a validation measures battery. The additional measures were chosen from published, validated measures and will assess patient symptom burden as well as the impact of disease on patient functioning and well-being to evaluate the concurrent validity for both the domains and the total score of the PLD-S and PLD-I as well. Additionally, measures/items required to assess known groups validity, retest reliability and assist in the interpretation of clinically meaningful difference for the measures, scores are included. The validation battery will be administered to patients/clinicians before other clinical assessments are completed.

7.3.4 Clinical Global Impression of Severity

The CGI-S scale provides an overall assessment of the current severity of the patient's symptoms. It is 1 of 3 domains of the clinician-rated instrument Clinical Global Impression scale (42), which is one of the most widely used assessment instruments in psychiatry. A modified version of the CGI-S will be used. The CGI-S will be completed at the time points indicated in Table 3.

7.4 Pharmacokinetic Assessment

7.4.1 Blood Collection and Handling

Blood samples for evaluation of plasma concentrations of octreotide will be collected from all patients at the time points indicated in Table 3. In exceptional cases where a blood sample for plasma octreotide concentration assessments cannot be taken, e.g., for logistic or patient personal reasons, this may be considered acceptable after agreement with the Sponsor.

Blood samples will be taken by either direct venipuncture or indwelling cannula inserted in a forearm vein.

The date and exact time of dosing, as well as the date and exact time of blood sampling, must be recorded on the eCRF. Detailed instructions for the collection, handling, and shipment of blood samples will be provided separately.

7.4.2 Analytical Method

Plasma concentrations of octreotide will be measured using a validated liquid chromatography-tandem mass spectrometry assay with a lower limit of quantification of approximately [REDACTED] ng/mL.

7.5 Pharmacodynamic Assessment

7.5.1 Blood Collection and Handling

7.5.2 Analytical Method

7.6 Safety Assessments

7.6.1 Adverse Events and Serious Adverse Events

7.6.1.1 Adverse Event Definitions

An **AE** (synonym: adverse experience) is defined as any untoward medical occurrence associated with the use of a drug in humans, in a patient or clinical trial subject administered a trial treatment and which does not necessarily have a causal relationship with this treatment (i.e., whether or not considered drug-related). An AE can, therefore, be any unfavorable and unintended sign (e.g., an abnormal laboratory finding), symptom, or disease temporally associated with the use of a trial treatment, whether or not considered related to the trial treatment. Patients will be instructed to contact the Investigator at any time after enrollment if any symptoms develop.

Adverse drug reaction: All untoward and unintended responses to a trial treatment assessed as related to any dose administered.

AEs or SAEs assigned a causality assessment by the Investigator of “probably related” or “possibly related” will be considered by the Sponsor to be related for the purpose of defining adverse drug reactions and thereby also expedited reporting.

An AE is considered “unexpected” if the nature, severity, or outcome is not consistent with the reference safety information section in the current edition of the IB (33).

An **AESI** is defined as an AE that, regardless of severity of causal relationship, is specifically of scientific and/or medical concern to the Sponsor’s product or program, and for which ongoing monitoring and rapid communication by the Investigator to the Sponsor may be appropriate. Such AEs may require further investigation in order to understand and characterize them.

AESIs are predicted by the underlying PLD disease, the mechanism of action of CAM2029, or observation with other substances in the same class as octreotide. Many but not all selected events have been observed in non-clinical studies and/or clinical trials with CAM2029 and are defined based on the continuously ongoing review of the safety data.

The selected AESIs are listed under the following mechanistic groups:

- Arrhythmogenic potential and QT prolongation AEs
- Gallbladder related AEs
- Gastrointestinal related AEs
- Injection site reactions
- Hyperglycaemia related AEs
- Liver and renal cyst infection
- Pyelonephritis

AESIs will be collected through routine AE collection.

An SAE is any untoward medical occurrence that at any dose:

- Results in death.
- Is life-threatening (an event in which the patient was at risk of death at the time of the event; it does not refer to an event which hypothetically might have caused death if it was more severe).
- Requires inpatient hospitalization or prolongation of existing hospitalization*.
- Results in persistent or significant disability or incapacity.
- Consists of a congenital anomaly or birth defect.
- Is another medically important event:
 - Important medical events that may not be immediately life-threatening or result in death or hospitalization but may jeopardize the patient or may require intervention to prevent one of the other outcomes listed in the definition above should also be considered serious. This is based on the medical and scientific judgment of the Investigator.

*Exemptions may be made when hospitalization is due to:

- Routine treatment or monitoring of the investigated indication, not associated with any deterioration in the condition.
- Elective or pre-planned treatment, for a pre-existing condition unrelated to the indication under investigation that did not worsen.
- Admission to a hospital or other institution for general care, not associated with any deterioration in the condition.

Other Reportable Information

Other reportable information describes the circumstances around the use of an IMP that potentially could provide knowledge of an IMP. These circumstances may or may not be associated with AEs or adverse drug reactions. Such information must be recorded, reported and followed up as indicated for an SAE (see [Section 7.6.1.3](#)). This includes:

- Pregnancy during exposure to a trial treatment. If a pregnancy is confirmed, the IMP must be discontinued immediately. Information about pregnancy exposure includes the entire course of pregnancy and delivery, and perinatal and neonatal outcomes, even if there are no abnormal findings. Both maternal and paternal exposures are considered other reportable information. For exposure involving the female partner of a male patient, the necessary information must be collected from the pregnant partner after obtaining informed consent.
- Medication errors
- Lactation exposure to an IMP
- Misuse, abuse or overdose of an IMP
- Inadvertent or accidental exposure to an IMP
- Any other use of the IMP outside what is describe in this protocol.

7.6.1.2 Eliciting, Documenting and Reporting of Adverse Events

The Investigator is responsible for ensuring that all AEs and SAEs are recorded on the AE page of the eCRF and reported to the Sponsor (see [Section 7.6.1.3](#) for reporting of SAEs). AEs will be

assessed from the time of signing the ICF until completion of all trial procedures and discharge from the trial. This includes any new event, sign or symptom occurring in the period between screening (after signing the ICF) and the first IMP administration on Day 1. If there is any doubt as to whether a clinical observation is an AE, the event should be reported.

Abnormal laboratory values shall be recorded as AEs if assessed as clinically significant by the Investigator. Laboratory abnormalities that are associated with an already reported medical condition will not be reported as separate AEs but will be used to assess the associated medical condition (e.g., increased neutrophil levels in case of reported infection or increased glucose in a patient with diabetes).

At every visit, patients will be asked a standard question to elicit any medically related changes in their well-being. They will also be asked if they have been hospitalized, have had any accidents, have used any new medications, or have changed concomitant medication regimens (both prescription and over-the-counter medications).

Information to be collected includes trial treatment, type of event, time of onset, dosage, Investigator-specified assessment of seriousness, severity and relationship to trial treatment, and time of event resolution, as well as any required treatment or evaluations, and outcome. AEs resulting from concurrent illnesses, reactions to concurrent illnesses, reactions to concurrent medications, or progression of disease states must also be reported. All AEs should be followed until they have reached a final outcome or the patient's participation in the trial ends, whichever comes first (see further details in [Section 7.6.1.7](#)).

The MedDRA will be used to code all AEs.

Any medical condition that is present at the time that the patient is screened but does not deteriorate thereafter should not be reported as an AE. However, if it deteriorates at any time during the trial, it should be recorded as an AE.

7.6.1.3 Reporting of Serious Adverse Events

Any AE that meets any of the SAE criteria ([Section 7.6.1.1](#)) must be reported to the Sponsor immediately (within 24 hours after the Investigator has become aware of the occurrence of the SAE), using the SAE eCRF page. If the eCRF page is unavailable, a paper copy of the SAE report form (available in the site binder) should be used, following the same timelines as for the electronic system. The Investigator will assess whether there is a reasonable possibility that the trial treatment caused the SAE and must sign the SAE report. Other reportable information as defined in [Section 7.6.1.1](#) should also be reported using the eCRF and followed up as indicated above for an SAE.

The following contact information is to be used for paper-based reporting of SAEs and other reportable information:

Email: [contact]

The Sponsor will be responsible for notifying the relevant regulatory authorities of any SAEs according to applicable legislation. The Investigator is responsible for notifying the IEC/IRB directly, as per IEC/IRB requirements.

7.6.1.4 Assessment of Severity

Severity is defined as a measure of the intensity of an AE or SAE and will be assessed according to the NCI CTCAE. If CTCAE grading does not exist for an AE, the severities of mild, moderate and severe, corresponding to Grades 1 through 3, will be used.

Changes in the severity of an AE should be documented to allow an assessment of the duration of the event at each level of intensity. An AE characterized as intermittent requires documentation of onset and duration of each episode.

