- ALT or AST levels $> 5 \times$ upper limit of normal for more than 2 weeks.
- Clinically significant and prolonged symptoms of reduced hepatic function, e.g., appearance of chronic fatigue, nausea, vomiting, right upper quadrant pain or tenderness, itchy skin, or swelling of legs and ankles.
- The patient is diagnosed with liver cirrhosis of Child-Pugh class C.
- The patient is diagnosed with hepatic decompensation with European foundation for the study of CLIF-C ACLF score 2 or 3 ([40](#)).

Re-challenge is not recommended when IMP treatment is discontinued due to the above criteria.

For details on follow-up of potential drug-induced liver injury cases, refer to [Section 17.1.1](#), Appendix 1.

Cyst-related Discontinuation Criteria

- Progression of extrahepatic cysts that, in the Investigator's opinion, may prevent the patient from safely participating in the trial.

Cardiac-related Discontinuation Criteria

- $\text{QT/QTcF} \geq 501 \text{ msec}$ or $> 60 \text{ msec}$ increase from baseline (average of triplicate ECG) after repeated triplicate measurement and as confirmed by central ECG reader.
- Torsades de Pointes
- Polymorphic ventricular tachycardia
- Signs/symptoms of serious arrhythmia
- Use of QT-prolonging medication with a known risk of Torsade de Pointes.
- Hypokalemia ($< 3.5 \text{ mmol/L}$) or hypomagnesemia ($< 0.7 \text{ mmol/L}$), or clinically significant hypocalcemia confirmed by repeated testing that is either a new finding or accompanied by vomiting or diarrhea and not corrected by treatment.

For details on QT prolongation management, refer to [Section 17.1.2](#) Appendix 1.

Hyperglycemia-related Discontinuation Criteria

- Patients with hemoglobin A1c $\geq 10\%$ at 3 consecutive visits (including unscheduled visits) despite prior appropriate management.

General Toxicity Discontinuation Criteria

- For ADRs with CTCAE grade 3, treatment should be delayed until the ADR resolves or improves to CTCAE grade ≤ 2 . If the ADR is expected to re-occur upon re-challenge, consider discontinuing IMP permanently. If ADR does not resolve or improve to CTCAE grade ≤ 2 (mild or moderate) within 28 days, IMP must be permanently discontinued.
- For AEs with CTCAE grade ≥ 4 regardless of relatedness to the IMP, treatment will be discontinued until further review.

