6.11 Stopping Rules

Based on the extensive safety data available for octreotide over 30 years, the use of CAM2029 in this trial is not expected to be a major concern. However, to ensure the safety of the patients the following stopping criteria will apply for the Double-Blind Treatment Period of the trial:

- More than 2 patients develop an ADR with CTCAE grade 3 or higher in the same preferred term (according to MedDRA).
- Two patients develop any ADR with CTCAE grade 4.
- One patient develops a grade 5 CTCAE.
- Two or more individual patients meet the IMP discontinuation criteria (see [Section 6.10.1](#)).

If all of the above stopping criteria are met or if new data become available that raise concern about the safety of the trial, no more patients will be dosed until the independent DMC has convened, evaluated all safety data from all patients and provided its recommendation as to whether the trial can continue, should remain on hold, or if other actions are warranted.

The DMC will provide their recommendation to the Sponsor, who will make a final decision on how to proceed. When the trial is on hold, no further dosing of any patient will be performed although patients will continue to follow the trial-specific visit schedule. More details about stopping rules and the DMC will be provided in the DMC Charter. See [Section 7.7](#) regarding the function of the DMC and [Section 11.3](#) regarding termination of the trial.

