7.6.1.7 Follow-Up of Adverse Events

All AEs should be followed until they have reached a final outcome (see [Section 7.6.1.5](#)) or the patient's participation in the trial ends, whichever comes first.

SAEs and Grade 3 (or severe), non-serious AEs that are assessed as "possibly related" or "probably related" to the IMP and that are still ongoing after ended trial participation, should be followed on a regular basis according to the Investigator's clinical judgment until a final outcome has been established.

The outcome "recovering" can be used as the final outcome for events that are stabilized (i.e., no further worsening is expected) and expected by the Investigator to resolve over time.

The outcome "not recovered" can be used as the final outcome for events that are not expected to resolve over time (e.g., cancer).

SAEs that are spontaneously reported by a patient to the Investigator after the patient has completed the clinical trial and for which a reasonable possibility of a causal relationship to the

IMP is assessed by the Investigator (“possibly” or “probably” related), should be reported to the Sponsor by the Investigator, regardless of the time that has elapsed (post-trial events).

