7.7 Data Monitoring Committee

A DMC will be established for this trial. The DMC will include 3 physicians, including 1 hepatologist. Up and until safety data from the last patient in the Double-Blind Treatment Period have been reviewed, the DMC will conduct periodic reviews of safety data and will continuously review all ADRs with CTCAE grade 3 and all AEs with CTCAE grades 4 or 5. The DMC will recommend actions to the Sponsor, as appropriate. The DMC will be informed to what extent the data and analyses provided to them have been quality controlled. Members of the DMC will not be involved in other trial-related tasks.

The DMC will be decommissioned after the safety data from the Double-Blind Treatment Period have been reviewed. The Sponsor will then be responsible for the continued safety monitoring during the remainder of the Open-Label Extension Period.

The DMC procedures are described in the DMC Charter.

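### The fallback severity scale ends at Grade 3, so a life-threatening or fatal event without CTCAE grading cannot reach the Grade 4 and 5 safety triggers; the loss is greatest for events judged not related

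*Protocol*

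**What the plan says.** Protocol 7.6.1.4 sets the main scale: "Severity is defined as a measure of the intensity of an AE or SAE and will be assessed according to the NCI CTCAE". It then gives a fallback. "If CTCAE grading does not exist for an AE", "the severities of mild, moderate and severe, corresponding to Grades 1 through 3, will be used". No category covers a life-threatening or fatal event. Section 7.6.1.7 confirms the equation of severe with Grade 3 in its wording "SAEs and Grade 3 (or severe), non-serious AEs".

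Three sections act on Grades 4 and 5:

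- **6.10.1**, general toxicity criteria: for AEs of CTCAE grade 4 or higher, "regardless of relatedness to the IMP, treatment will be discontinued until further review". At Grade 3 the section covers ADRs only, and the action is a dosing delay.
- **6.11**, stopping rules for the Double-Blind Treatment Period: one criterion counts two patients with a grade 4 ADR. Another reads "One patient develops a grade 5 CTCAE" and is not limited to ADRs.
- **7.7**: the DMC "will continuously review all ADRs with CTCAE grade 3 and all AEs with CTCAE grades 4 or 5".

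SAP 5.10.1 says that all AEs are graded by CTCAE. It does not mention the fallback and adds no mapping to Grade 4 or 5.

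**The concern.** The scale and the rules that depend on it do not fit together. A site that follows 7.6.1.4 to the letter records Grade 3 for a life-threatening or fatal event with no CTCAE grading, and the rules written for such events then do not apply to it.

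This matters most where relatedness is in doubt. Sections 6.10.1 and 7.7 cover unrelated events at Grades 4 and 5 but only ADRs at Grade 3. Section 7.6.1.6 lets an event be called not related when the underlying disease is a plausible explanation. A serious complication attributed to the liver disease could therefore lose the any-causality protection through the severity scale alone.

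There is also an effect on reporting. The SAP's row for TEAEs by CTCAE grade would understate the severity of such an event. The SAP's rows for Grade 3 or higher would still include it, if it falls in the groups they cover.

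**Working it through.** No arithmetic applies beyond comparing grades, so the check sets the sections side by side.

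**Step 1: ceiling of the fallback.** The highest grade available under 7.6.1.4 without CTCAE grading is 3.

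**Step 2: thresholds.** The discontinuation rule needs 4 or higher, the two stopping criteria need 4 and 5, and any-causality continuous DMC review needs 4 or 5. All exceed 3.

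**Step 3: any link other than grade?** None of these rules is worded by seriousness or outcome. The life-threatening criterion (7.6.1.1) and the Fatal outcome code (7.6.1.5) exist, but no text converts them into a grade.

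**Step 4: what each kind of event loses.** The grade 4 stopping criterion covers ADRs only, so an unrelated event loses nothing there. After a death, discontinuing or delaying that patient's dosing is moot.

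| Event without CTCAE grading | Lost through the Grade 3 ceiling | Grade-based provisions that remain |
|---|---|---|
| Life-threatening, not related | Discontinuation rule; continuous DMC review | None |
| Fatal, not related | Grade 5 stopping criterion; continuous DMC review | None |
| Life-threatening, related | Discontinuation rule; count toward the grade 4 stopping criterion | Grade 3 delay rule; first stopping criterion (Grade 3 or higher, same preferred term); continuous DMC review |
| Fatal, related | Grade 5 stopping criterion | First stopping criterion; continuous DMC review |

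**Step 5: how the stopping criteria combine.** Section 6.11 lists four criteria. As written, its criteria-based hold needs all four, with new safety information as the alternative route. One count that cannot be reached is then enough to block the criteria-based hold. The fourth criterion counts patients who meet the 6.10.1 discontinuation criteria, so an event that misses the Grade 4 rule there may drop out of that count too.

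**Step 6: duration.** The stopping criteria apply to the Double-Blind Treatment Period, and the DMC is decommissioned after its review of that period. The end of 6.10.1 carries the general toxicity criteria into the Sponsor's monitoring of the extension. The gap in the discontinuation rule therefore continues through the 120-week extension.

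**The case against.** The strongest reply is that few events, perhaps none, are affected and that much else protects these patients.

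- **Reach.** Neither document lists an AE without CTCAE grading, and the SAP speaks of grading all AEs by CTCAE. A reader might infer that cyst haemorrhage, rupture or infection lack a CTCAE entry. The documents name these complications but do not say how they are graded. This part of the objection stands: the frequency is unknown. Even so, 7.6.1.4 itself provides for ungraded events, and for those its scale is too short.
- **Other safeguards.** A reader might infer that such events escape oversight. They do not. SAEs reach the Sponsor within 24 hours (7.6.1.3), and the outcome code records death. The Investigator may discontinue treatment on judgment (6.10.1), the DMC reviews safety data periodically (7.7), and new safety information can prompt a hold (6.11). The SAP also has separate rows for serious TEAEs and TEAEs leading to death. This stands, but none of these supplies the grade that the rules in question require.
- **Related events.** It would be wrong to say that every ungraded event misses DMC review. A related one at Grade 3 is still reviewed continuously.
- **Follow-up after the trial.** A reader might see the same gap in 7.6.1.7, which names Grade 3 but not Grade 4 non-serious events. That does not follow from the fallback. A life-threatening or fatal event is serious by definition, and that section already follows related SAEs. Any gap for non-serious events that CTCAE itself grades 4 is a separate question.
- **Timing.** Protocol 4.3 planned the last patient's first visit for Q4 2023. Adding up to 12 weeks of screening and 52 weeks of treatment (64 weeks) to the end of that quarter gives about late March 2025. The SAP dates protocol version 8 to 29-Jan-2025. If the planned dates held, little of the double-blind period remained. Actual dates are not given, and the extension would still be affected.
- **DMC Charter.** Section 6.11 leaves further stopping-rule detail to the Charter, which is not among the documents and may address this.

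**Conclusion.** The inconsistency is real and follows from the text alone. For an AE without CTCAE grading, the highest permitted grade is one below the lowest grade that the discontinuation rule and the any-causality DMC review require.

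For events judged not related, a life-threatening event misses two provisions (discontinuation rule, continuous DMC review) and a fatal event misses two (grade 5 criterion, continuous DMC review), with no other grade-based provision left. Related events lose less: they keep continuous DMC review and the Grade 3 provisions that still have meaning, but do not count toward the grade 4 or grade 5 stopping criteria. Because 6.11 requires all its criteria to be met, that missing count can matter.

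The documents do not support the stronger reading that these events go unseen or that all Grade 4 and 5 rules fail equally for every such event. The conclusion assumes that sites apply 7.6.1.4 as written, that at least some AEs lack CTCAE grading, and that the Charter or site instructions do not already close the gap. It is worth correcting because the change is cheap, not because the gap is known to be frequent.

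**What to change.** Reconcile 7.6.1.4 with 6.10.1, 6.11 and 7.7 so that the fallback severity scale covers every grade the triggers use. One way is to tie its upper levels to the life-threatening criterion in 7.6.1.1 and the Fatal outcome in 7.6.1.5. Carry the same wording into SAP 5.10.1, which is now silent on the fallback. Add a data check that flags disagreement between severity grade, seriousness and outcome. The clinical rules themselves, meaning when treatment is delayed or discontinued and when the trial is held, stay as written.

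The cost is a short protocol and SAP edit, possibly a change to the eCRF severity list, and minor re-coding of events already entered. Seriousness and outcome are already recorded under 7.6.1.2, so no new data collection should be needed, assuming the SAE record shows which seriousness criterion was met. Any re-coding for the double-blind period should be done before unblinding, if that is still possible.
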